In this application, we describe a pilot study to determine if this treatment is of any benefit in treating hypoglycemia unawareness and to collect the observations necessary to develop a full-scale clinical trial of sufficient power to address our hypothesis. Our specific aim is to perform a randomized double blind trial of four weeks of naltrexone or placebo therapy in twenty subjects with type 1 diabetes and hypoglycemia unawareness and compare the outcome measures collected before treatment with those collected at the end of the treatment period.

Background and significance

Hypoglycemia unawareness is a limiting factor in the treatment of type 1 diabetes. Lack of awareness of hypoglycemia increases the risk for severe hypoglycemia, coma, and death during insulin therapy (5) and fear of hypoglycemia may prevent patients from optimally controlling their blood sugars, thereby increasing their risk for the development of diabetes complications. Strict avoidance of hypoglycemia has been known to partially restore awareness of hypoglycemia (6), however it is very difficult to achieve. Using PET, Dunn et al (1) have reported an increase in glucose uptake (a measure of activation) in brain regions associated with motivation (ventral striatum) and reward perception (lateral orbitofrontal cortex) and decreased activation of stress related regions (amygdala) during hypoglycemia in hypoglycemia unaware subjects with type 1 diabetes relative to hypoglycemia aware subjects with type 1 diabetes. This activation pattern resembles that seen in response to substances with addictive potential (7, 8), raising the question of whether one of the reasons that hypoglycemia unawareness is so difficult to reverse is that it is rewarding and not perceived as a stress to the patient.

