Most relevant to this application is our experience performing hypoglycemic clamp studies while brain activation is studied using magnetic resonance techniques. In our laboratory, we have used continuous arterial spin labeling (CASL) to identify brain regions that are activated in response to insulin-induced hypoglycemia in healthy human subjects (23). Five men and five women (age 29 ± 10 yrs, BMI 23.3 ± 2.1 kg/m², mean \pm SD) participated in this study. CASL images were acquired at euglycemia (99 ± 5 mg/dl) and again during hypoglycemia (52 ± 3 mg/dl) using 2D GE-EPI (labeling time=2500 ms, resolution = $2 \times 2 \times 3$ mm, 100 label/control pairs). In whole brain analysis, increases in regional cerebral blood flow, a measure of neuronal activation, were noted during hypoglycemia relative to euglycemia bilaterally in the medial thalamus, anterior cingulate, and posterior cingulate using BrainVoyager software, as has also been demonstrated by Teves et al using PET (TEVES PNAS 2004). These increases coincided with the peak responses in counterregulatory hormones (glucagon = 110 ± 41 pg/ml, epinephrine = 519 ± 273 pg/ml, norepinephrine = 405 ± 124 pg/ml), providing evidence that activation of these brain regions is involved in the counterregulatory response to hypoglycemia. Focused region of interest analysis of specific regions such as the hypothalamus or amygdala was not performed in this study, but will be performed in the proposed project.

Research Design and Methods:

This study will be a randomized double blind placebo controlled trial involving 20 subjects with type 1 diabetes and hypoglycemia unawareness. Since the time necessary for the effect of naltrexone on our outcome variables to washout after a treatment period is unknown, each subject will serve as their own control and differences between the changes in the outcome measures will be evaluated between groups. The study design is depicted in the figure below.

Subjects

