Subjects will be admitted to the research center the afternoon before the hypoglycemic clamp study on day zero. They will be allowed to take their short acting insulin or a bolus via their pump with their evening meal, but their evening dose of long-acting insulin or their pump will be held after 6 PM. Blood glucose values will then be monitored every 1-2 hours and an intravenous infusion of insulin and/or glucose will be provided to maintain blood sugars between 100-150 mg/dl. Subjects will not be given additional food after their evening meal until the end of the hypoglycemic clamp on day zero.

On the morning of the study, subjects will be transferred to the Center for Magnetic Resonance Research. After their arrival, they will be prepared for clamp study by the placement of one intravenous catheter into one vein in each antecubital fossa for the later infusion of glucose, insulin, and potassium. A third intravenous catheter will be placed retrograde into a vein in the distal leg for later blood sampling. Baseline blood samples for glucose, glucagon, catecholamines, cortisol, and

growth hormone will then be collected no sooner than 30 minutes after catheter placement. At time 0 a constant infusion of insulin will be started at 2.0 mU/kg/min and the subject will be placed into the magnet. Plasma glucose be initially maintained at euglycemia (~100 mg/dl) while the baseline scan is done. Plasma glucose will than be reduced to 50 mg/dl and maintained at this level of glycemia for approximately thirty minutes. During the final 15 minutes subjects will be asked to quantitate their symptoms using a standardized method (25). Blood samples will be obtained every five minutes for measurement of plasma glucose concentration on a nearby analox machine and every twenty minutes for later measurement of glucagon, catecholamines, cortisol, and growth hormone.

Study design. CGMS= continuous glucose monitoring; BG=blood glucose; CASL = continuous arterial spin labeling; hypo= hypoglycemic; safety labs = ALT, AST, Cr, CPK

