Investigational New Drug (IND) approval for the use of this medication for this study has already been obtained from the Food and Drug Administration. The investigational pharmacy at the University of Minnesota Medical Center will insure that the naltrexone and placebo tablets are identical in appearance and will maintain the log of the treatment assignment. Only the study pharmacist will have access to this log until the study is completed. The dose of the drug will be titrated up over 10 days (25 mg daily x 5 days, then 50 mg daily x 5 days, then 50 mg BID x 18 days). Subjects will be asked to avoid use of acetaminophen, non-steroidal anti-inflammatory medications and alcohol while taking naltrexone. At 14 ± 1 days, subjects will return to provide blood for measurement of ALT, AST, CPK, and creatinine. Drug will be stopped in subjects who experience an increase that exceeds two times the upper limit of normal for ALT, AST, or CPK or have a rise in their creatinine to 2.0 mg/dl or above in men or 1.5 mg/dl or above in women.

At the 14 day visit, subjects will be reminded to wear the continuous glucose monitor for the seven days before the next hypoglycemic clamp study and will be sent home with sufficient supplies to do so. On the night before the clamp study, they will be readmitted to the research center for preparation as outlined above. Repeat samples for ALT, AST, CPK, and creatinine will also be collected. On the day of the study, subjects will take their final dose of naltrexone/placebo and be transported to the Center for Magnetic Resonance Reserch to repeat the clamp study with measurement of cerebral blood flow described above.

Statistical analysis

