This is a pilot study in which a sample size of 20 (10 subjects to receive placebo and 10 subjects to receive naltrexone) was arbitrarily selected to determine how large a sample size will be necessary to determine if naltrexone has an effect on our outcome measures. Each subject will serve as his/her own control and changes in the outcome variables (number of hypoglycemic events defined as number of episodes of hypoglycemia that require the assistance of another to recognize/treat and as minutes during which blood glucose is < 70 mg/dl as measured by continuous glucose monitoring, both over a 7 day period); symptom scores collected during hypoglycemia' and differences in regional blood flow noted between the euglycemic and hypoglycemic conditions for each study), will be compared between pre-treatment and end of treatment periods using Student's t-test with correction for repeated measures. [name] from the Department of Biostatistics at the University of MInnesota will assist in the statistical analyses.

Anticipated problems/potential solutions

The most significant problem we may encounter is that our treatment outcomes will be unaffected by naltrexone treatment. Originally, we intended to focus on the effect of naltrexone on cerebral blood flow as a measure of regional activation during hypoglycemia, but since we are unaware of data that demonstrate naltrexone alters brain activation patterns in addicts, we have broadened our outcome measures to include more clinically relevant information such as frequency of hypoglycemia and symptom scores during controlled hypoglycemia. We are hopeful that naltrexone will have an effect on at least one of the outcome variables and will use the data collected from this pilot to design a larger study.

4. Sinclair JD. Evidence about the use of naltrexone and for different ways of using it in the treatment of alcoholism. *Alcohol Alcohol* 2001;36(1):2-10.

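### The only named test compares before with after treatment; no test is given for naltrexone versus placebo, although the design section promises a between-group comparison

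*Combined protocol and SAP*

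**What the plan says.** Three places in the protocol describe the comparison.

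- **Specific aim** (opening section, before Background and significance). The study is a "randomized double blind trial of four weeks of naltrexone or placebo therapy in twenty subjects", and the aim is to "compare the outcome measures collected before treatment with those collected at the end of the treatment period". Both arms are named, but the contrast is before versus after.
- **Research Design and Methods.** Here "each subject will serve as their own control and differences between the changes in the outcome measures will be evaluated between groups". This is a between-arm contrast, with no test named.
- **Statistical analysis.** The allocation is given ("10 subjects to receive placebo and 10 subjects to receive naltrexone"), and the changes in the outcomes "will be compared between pre-treatment and end of treatment periods using Student's t-test with correction for repeated measures". This is the only test named anywhere, and arm is not a side of the comparison.

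The Statistical analysis section also gives the purpose of the pilot: "to determine how large a sample size will be necessary to determine if naltrexone has an effect on our outcome measures".

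**The concern.** A paired before/after comparison estimates the drug effect plus whatever else changed over the four weeks. The placebo arm exists to remove that second part, and the named test does not use it for that purpose.

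Shared change is possible in this design. Every subject rates symptoms during the clamp ("During the final 15 minutes subjects will be asked to quantitate their symptoms using a standardized method") and later returns to "repeat the clamp study with measurement of cerebral blood flow described above", so familiarity with the procedure could move the scores in both arms. The request to abstain from alcohol applies only in the treatment period, so it too could act on both arms. The documents do not say how large such a change would be or which way it would go.

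A favourable shared change would be credited to naltrexone; an adverse one could hide a real benefit. Because the pilot is meant to inform the size of a later trial, either error could carry over into that trial.

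**Working it through.** **1. Can the named test be read as a between-arm test?** The sentence takes changes as its subject and then compares them between two periods. A pre-to-end change cannot itself be compared between pre-treatment and end of treatment, so the sentence has to be reinterpreted before it can be run. The readings that keep its stated contrast are all paired:

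- all 20 subjects pooled (the sentence restricts to neither arm);
- the naltrexone arm alone (n=10);
- each arm separately (n=10 each).

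None yields a test of naltrexone against placebo. The repeated-measures phrase does not say what is corrected and does not bring in arm. Nowhere does the document give a two-sample test on change, an ANCOVA or a group-by-time term.

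**2. Inputs.** From the Statistical analysis section: 10 subjects per arm, a number the protocol calls arbitrary, so there is no sample-size calculation to reproduce. Assumed, because the documents do not state them: two-sided alpha 0.05, normal changes with equal SD in both arms, and every shift and effect below. The unit is the SD of change.

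**3. No drug effect, shared shift s.** The paired test has noncentrality s√n on n−1 df. In the two-sample test on changes the shift cancels, so its rejection rate is 5% whatever s is (0.049 to 0.051 in 200,000 simulations).

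| Shared shift s | Paired, naltrexone arm (n=10) | Paired, pooled (n=20) | Between arms (10 v 10) |
|---|---|---|---|
| 0 | 5% | 5% | 5% |
| 0.25 | 11% | 19% | 5% |
| 0.5 | 29% | 56% | 5% |
| 0.8 | 62% | 92% | 5% |
| 1.0 | 80% | 99% | 5% |

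**4. Real benefit of 1.0 SD, adverse shared shift.** Chance of a significant result in the direction of benefit. The paired columns are from 200,000 simulations; the between-arm power is exact, with noncentrality 1.0 × √(10/2) = 2.24 on 18 df.

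| Adverse shift | Naltrexone arm | Pooled | Between arms |
|---|---|---|---|
| 0 | 80% | 47% | 56% |
| 0.25 | 56% | 13% | 56% |
| 0.5 | 29% | 1% | 56% |
| 0.8 | 8% | <0.1% | 56% |

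Pooling also halves the drug effect, because half the subjects take placebo: (1.0 + 0)/2 = 0.5 SD.

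**5. Sizing the next trial.** Suppose a naltrexone-arm before/after effect of 0.8 SD is taken as the drug effect. A two-sample t-test with 80% power then needs 26 per arm.

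- If 0.25 SD of it is a favourable shared change, the drug effect is 0.8 − 0.25 = 0.55 SD. That needs 53 per arm, and 26 per arm give 49% power.
- If the shared change is 0.25 SD adverse, the drug effect is 0.8 + 0.25 = 1.05 SD, and 16 per arm would be enough.

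**6. What the between-arm test costs in precision.**

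- Effect detectable with 80% power: 1.00 SD for the paired test (n=10), 1.32 SD between arms (10 v 10).
- 95% CI half-width: paired 2.262/√10 = 0.72 SD; between arms 2.101 × √(2/10) = 0.94 SD.
- ANCOVA on the baseline value (17 df, variance ratio (1+ρ)/2, chance-imbalance factor 1 + 1/16): detectable effect 1.10, 1.19 and 1.26 SD at assumed pre/post correlations ρ of 0.3, 0.5 and 0.7.

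**The case against.** The strongest reply is that the right comparison is already in the plan. Research Design and Methods states the difference in change between groups, the trial is blinded and placebo-controlled, and a biostatistician is assigned. On this view the Statistical analysis sentence is a loose restatement, and the defect is one of wording. This is a fair account of the likely intent, and it limits the harm to the case where the analysis section is followed as written. It does not remove the conflict: the aim and the analysis section both state before versus after, and the only named test is attached to that contrast.

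Three further points have some force.

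- **Readings.** The sentence is not coherent enough to make the pooled analysis the certain reading. Separate paired tests in each arm would at least display any shared change. They would still not test the difference between arms, and the n=10 figures apply to each of them.
- **Sizing.** The protocol gives no method for sizing the later trial, so step 5 is conditional. A shared additive shift also leaves the within-arm SD of change, a main planning input, intact.
- **Assumptions.** Every shift is assumed, and normality is doubtful for assisted episodes counted over 7 days, so the rates may not carry over to that outcome.

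Pilot status excuses low power. It does not excuse a contrast that leaves out the randomised comparison.

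**Conclusion.** The concern holds: the analysis section is wrong as written and should be fixed. That the design section promises a between-group comparison and the only named test does not make one rests on the text alone and is firm.

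The size of the consequence is conditional on the assumed alpha, normality, equal SDs and shared shift. Under those assumptions a moderate shared change of 0.5 SD raises the false-positive rate from 5% to 29% (naltrexone arm) or 56% (pooled). If adverse, it cuts the chance of finding a 1.0 SD benefit in the naltrexone arm from 80% to 29%. With no shared change the false-positive rate stays at 5%. The design and the planned data support the correct analysis.

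**What to change.** Replace the comparison sentence in the Statistical analysis section with wording such as:

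> For each outcome, the change from the pre-treatment to the end-of-treatment assessment will be compared between the naltrexone and placebo groups with a two-sample t-test on the changes. The between-group difference will be reported with its 95% confidence interval. Within-group changes are descriptive only.

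For continuous outcomes, ANCOVA of the end value adjusted for the pre-treatment value is an acceptable alternative; choose one in advance. For the assisted-episode count, a permutation version of the between-group comparison avoids relying on normality. State what the repeated-measures correction is meant to do, or delete it. Align the comparison clause of the specific aim with Research Design and Methods.

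For planning the next trial, report the between-arm difference and the SD of change, each with its confidence interval. Do not size that trial from a before/after effect or from the pilot point estimate alone. With 10 per arm and a true effect of 0.55 SD, the observed standardised effect ranges from −0.34 to 1.58 (central 95%) and has the wrong sign in 11% of pilots. The 95% interval for the SD of change (18 df) runs from 0.76 to 1.48 times its estimate.

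The cost is one reworded paragraph and one clause of the aim, with no added visits or measurements, plus the loss of precision shown in step 6, part of which baseline adjustment recovers.

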NCT01053078

Naltrexone and Hypoglycemia in Type 1 Diabetes

Protocol Approval Date: August 17th, 2012

PI: [name]

Hypoglycemia unawareness is a limiting factor in the treatment of type 1 diabetes and is a very difficult problem to reverse. Using positron emission tomography (PET), Dunn et al have recently demonstrated that patients with type 1 diabetes and hypoglycemia unawareness display a brain activation pattern during hypoglycemia that resembles the activation pattern seen following the administration of an addictive substance such as cocaine (1). In this response, the amygdala and hypothalamic regions associated with stress were less activated and the ventral striatum region associated with motivation and the lateral orbitofrontal cortex region associated with reward were not activated as strongly during hypoglycemia in the unaware compared to the aware subjects. These observations raise the question of whether one reason hypoglycemia unawareness is so difficult to reverse is that it is rewarding and not perceived as a stress to the patient, much like the response an addict has to a drug upon which he has grown dependent. If so, therapies applied to the treatment of addictions might provide a novel approach to the treatment of hypoglycemia unawareness in type 1 diabetes. One such therapy could be the orally administered non-addicting opioid antagonist naltrexone that has been shown to be effective in the treatment of many addictions (2-4).

The long-term goal of this project is to test the hypothesis that naltrexone therapy in subjects with type 1 diabetes and hypoglycemia unawareness will:

- reduce the number of hypoglycemic events (defined as number of episodes of hypoglycemia that require the assistance of another to recognize/treat and as minutes during which blood glucose is < 70 mg/dl as measured by continuous glucose monitoring, both over a 7 day period),
- improve recognition of hypoglycemia during experimental conditions, and
- reduce activation in the ventral striatum and lateral orbitofrontal cortex and increase activation in the amygdala and hypothalamus during hypoglycemia.

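### Does a pilot with at least seven unranked outcomes need a named lead outcome or a multiplicity rule?

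*Combined protocol and SAP*

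**What the plan says.** The Statistical analysis section lists episodes needing another person's help, minutes below 70 mg/dl on continuous monitoring (both over seven days), symptom scores during the clamp, and differences in regional blood flow. It does not name the regions. The opening summary does, with directions: "reduce activation in the ventral striatum and lateral orbitofrontal cortex and increase activation in the amygdala and hypothalamus during hypoglycemia". The Experimental protocol section repeats the same four as examples, so that list is formally open.

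Two purposes appear. The specific aim describes "a pilot study to determine if this treatment is of any benefit in treating hypoglycemia unawareness". The Statistical analysis section says that 20 subjects, 10 per arm, were chosen arbitrarily "to determine how large a sample size will be necessary to determine if naltrexone has an effect on our outcome measures".

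On method, the same section says "Each subject will serve as his/her own control" and that pre-treatment and end-of-treatment values will be compared "using Student's t-test with correction for repeated measures". No significance level, sidedness, success criterion or outcome ranking is given anywhere.

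On how the list arose, the anticipated-problems section says "Originally, we intended to focus on the effect of naltrexone on cerebral blood flow as a measure of regional activation during hypoglycemia", explains that "we have broadened our outcome measures to include more clinically relevant information such as frequency of hypoglycemia and symptom scores during controlled hypoglycemia", and adds "We are hopeful that naltrexone will have an effect on at least one of the outcome variables". The same sentence goes on to say that the pilot data will be used to design a larger study.

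**The concern.** Three features together look troubling. A single focus gave way to a longer list with nothing put in its place as lead. The aim speaks of any benefit, and the authors hope for an effect on at least one outcome, which invites a reader to treat any one significant result as success. The only correction mentioned follows a sentence about subjects being their own controls, so it most naturally refers to within-subject pairing and does not deal with the number of outcomes.

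If the results were used that way, a chance finding could be reported as evidence that naltrexone helps. The sizing purpose raises a similar worry: each outcome implies its own sample size for the next trial, and the plan does not say which one will be carried forward.

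**Working it through.** **Reproducing a stated figure.** There is none to reproduce. The total of 20 is described as arbitrary and matches 10 + 10. No alpha, power, effect size or family-wise error rate is given.

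**Counting outcomes.** Assisted episodes (1) + minutes below 70 mg/dl (1) + symptom score (1) + four regions (4) = 7. Four of these belong to the earlier blood-flow focus, so the broadening added three.

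**Assumptions, none of them in the plan.** No true effect; each outcome tested at two-sided 0.05, which is 0.025 in the predicted direction; normal changes; between-group t-test with 10 per arm (18 df); one common correlation from 0 to 0.8. Predicted directions come from the opening summary: four down (assisted episodes, minutes below 70 mg/dl, ventral striatum, orbitofrontal cortex) and three up (symptom score, amygdala, hypothalamus).

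**Chance of at least one false positive.** For k independent tests at level a, this is 1 − (1 − a)^k. Values at correlation 0.8 are by simulation.

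| Set of outcomes | Independent | Correlation 0.8 |
|---|---|---|
| Seven, two-sided | 1 − 0.95^7 = 30.2% | about 15–16% |
| Seven, predicted direction | 1 − 0.975^7 = 16.2% | about 11% |
| Three clinical, predicted direction | 1 − 0.975^3 = 7.3% | about 6.5% |
| One lead, predicted direction | 2.5% | 2.5% |

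The two-sided row counts significant harm as a success, so it does not fit a question about benefit. The predicted-direction rows do. The 11% depends on the predicted signs being mixed while all raw correlations are positive; with aligned signs it is about 8%. The three-outcome row is relevant because the specific aim concerns benefit in treating unawareness, and the plan itself sets the clinical measures apart from blood flow.

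**Dependence on the comparison.** These figures hold for a between-group test. A pre-versus-end test within one arm can exceed them, because outcomes may drift without any drug effect. Suppose a drift of 0.25 SD, in the predicted direction, in the two hypoglycemia outcomes only, with n = 10, 9 df and independent outcomes. The noncentrality is 0.25 × √10 = 0.79. Each of those two tests then rejects with probability 0.109 two-sided, or 0.106 in the predicted direction.

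- Two-sided: 1 − 0.95^5 × (1 − 0.109)^2 = about 39%.
- Predicted direction: 1 − 0.975^5 × (1 − 0.106)^2 = about 30%.

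Most of that excess comes from the lack of a control comparison, and ranking the outcomes would not remove it.

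**Sizing.** Even if all seven outcomes truly needed the same n, pilot variances on 18 df would give a largest-to-smallest ratio with median 2.46 (correlation 0) to 1.72 (correlation 0.8). A single lead outcome is estimated just as imprecisely. The 95% chi-square limits on 18 df are 8.23 and 31.53, so the required n runs from 18/31.53 = 0.57 to 18/8.23 = 2.19 times the planned figure.

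**The case for a change.** The best case for a change is that it would cost a few sentences and that sizing is the pilot's own stated purpose. With several candidate sample sizes and no rule for choosing among them, the next trial could be built on whichever outcome looked best. The wording about any benefit and at least one outcome makes an opportunistic reading foreseeable, and nothing in the plan excludes it. Only the study pharmacist can see the treatment log until the study is completed, so the investigators could still name a lead outcome while blind.

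Part of this stands. The outcomes are unranked, the region list is formally open, and the arithmetic is sound under its assumptions. Three points weaken the rest.

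- The hope for one effect is worded as a hope and tied to designing a larger study; it is not a success criterion.
- Using a pilot to learn which outcome is feasible and stable enough to lead a larger trial is ordinary practice. Fixing the choice beforehand gives up some of what the pilot is for.
- Naming a lead before the log is opened would protect a between-group test only. Under a literal pre-versus-end comparison the pooled changes are visible while assignment is still blind.

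**Conclusion.** No change is called for. The plan leaves out a detail that a confirmatory trial would need, but no stated rule or figure is shown to be wrong. The inflated error rate (about 11% to 16% for seven outcomes in the predicted direction, about 7% for the three clinical ones, against 2.5%) applies only if one nominally significant result is read as benefit, and the plan sets no such rule. It also rests on an assumed 0.05 level, an assumed correlation range and a between-group test.

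The gap is one that analysts would fill sensibly: test the four regions already named with directions in the opening summary, report every outcome as exploratory with a 95% confidence interval, and choose the next trial's lead outcome on clinical and practical grounds. If the investigators do want a lead outcome in this pilot, the choice is safe only if made before any end-of-treatment outcome data are examined. Whether the test is between groups, as in Research Design and Methods, or pre versus end, as in Statistical analysis, is a separate question that this point does not settle.
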